13.4.3 Future research & drug policy implications.....	27
13.5 ALTERNATIVES TO STUDY PARTICIPATION.....	27
13.6 COMPENSATION.....	27
13.7 PARTICIPANTS CONFIDENTIALITY	28
13.8 INSURANCE ARRANGEMENT	28
14. LABORATORY SPECIMENS & PRACTICE	28
14.1 LABORATORY SPECIMENS	28
14.2 QUALITY CONTROL AND QUALITY ASSURANCE.....	29
14.3 SPECIMEN STORAGE	29
14.4 SPECIMEN TRANSPORT.....	29
15. ADMINISTRATIVE PROCEDURES.....	29
15.1 DATA MANAGEMENT	29
15.2 RECORD RETENTION.....	30
15.3 USE OF INFORMATION AND PUBLICATIONS.....	30
16. REFERENCES	31
17. APPENDIX A: THAI NATIONAL GUIDELINE FOR PREVENTION OF MATERNAL-TO-CHILD TRANSMISSION OF HEPATITIS B	34
18. APPENDIX B: STUDY FLOW.....	35
19. APPENDIX C: SCHEDULE OF STUDY PROCEDURES	36
20. APPENDIX D: AMENDMENT HISTORY	37

Table of Abbreviations

ALT	Alanine transaminase
ARVs	Antiretrovirals
AUC	Area Under Curve
CRF	Case Report Form
DNA	DeoxyriboNucleic Acid
DOT	Directly Observed Treatment
EGA	Estimated Gestational Age
GCP	Good Clinical Practice
HB	Hepatitis B
HBeAg	Hepatitis B e antigen
HBIG	Hepatitis B immunoglobulin
HBsAg	Hepatitis B s antigen
HBV	Hepatitis B virus
HIV	Human Immunodeficiency Virus
ICF	Informed Consent Form
MTCT	Mother to child transmission
OXTREC	Oxford Tropical Research Ethics Committee
PI	Principal Investigator
PIL	Participant/ Patient Information Leaflet
PK	Pharmacokinetics
PMTCT	Prevention Mother to child transmission
REC	Research Ethics Committee
SOP	Standard Operating Procedure
SMRU	Shoklo Malaria Research Unit
TDF	Tenofovir disoproxil fumarate
TFV	Tenofovir

1. Synopsis

Study Title	The pharmacokinetic parameters of tenofovir (TFV) in maternal blood and breast milk in women treated with daily Tenofovir Disoproxil Fumarate (TDF; 300mg) for prevention of mother to child transmission (PMTCT) of hepatitis B virus (HBV) mono-infection.	
Internal ref.no.	VIR19001	
Study Design	Prospective descriptive dense pharmacokinetics study of Tenofovir (TFV) in 24 migrant pregnant women treated with Tenofovir disoproxil fumarate (TDF) to prevent mother to child transmission of Hepatitis B.	
Study Participants	Women with viable pregnancy with HBV mono-infection	
Planned Sample Size	24 pregnant women – 12 will enroll in 2 nd trimester (T2) and 12 in 3 rd trimester (T3)	
Planned Study Period	August 2019 - August 2021	
	Objectives	Outcome Measures
Primary	To measure the dense PK parameters of TFV in a steady-state during three gestational periods in TDF treated HBV mono infection	PK parameter profiles in maternal blood
Secondary	1. To investigate the TFV concentration , breastmilk and infants	- Maternal breastmilk TFV concentrations - Milk to maternal plasma concentration ratios (M/P) - Infant plasma drug concentration
	2. To investigate if/when HBV DNA is detected in blood and breastmilk after cessation of TDF.	HBV DNA in blood and breastmilk

2. Introduction – Background and Prior Research

Hepatitis B virus (HBV) can be asymptomatic for years but can also lead to chronic disease, cancer and hepatitis, hepatocellular carcinoma, and liver failure be eradicated with the current therapy. (1-3) Chronic maternal Hepatitis B virus (HBV) infection is an important source of perinatal transmission in regions of high HBV prevalence. In antenatal clinics at Shoklo Malaria Research Unit (SMRU), the Hepatitis B (HB) surface antigen (sAg) prevalence is 8.3% with a HB e-antigen (HBeAg) prevalence of 32.7% in those positive for HBsAg in 2012-2014.(4) Perinatal infection occurs in 70–90% of women with HBeAg positive chronic HBV compared with 0–30% in those with HBeAg negative chronic HBV (inactive carriers).(1) These infection rates reflect, in part, the failure of maternal and child health programs to prevent perinatal transmission with hepatitis B immunoglobulin (HBIG) and HB vaccines. Prevention of mother to child transmission (PMTCT) fails in an estimated 8–32% of cases with adequate preventive techniques.(5, 6) Antiretrovirals (ARVs), like Tenofovir Disoproxil Fumarate (TDF) are active against HBV and may reduce the risk of HBV transmission at birth if offered at the right time in pregnancy.(7-9)

One of the major gaps in implementing this strategy is adequate pharmacokinetic (PK) data in pregnant women that informs correct dosing. One recently published population PK study in 154 women who provided single maternal blood samples (32 and 36 weeks of pregnancy, at delivery, and at 1 and 2 months postpartum) reported a tenofovir area under curve (AUC) 0–24 that was estimated to be 20% (95% CI, 19-21%) lower during pregnancy than during postpartum suggesting no dose adjustments are needed in 3rd trimester.(10) Most PK studies for TDF in pregnancy have been for Human Immunodeficiency Virus type 1 (HIV) infections. However, these patients often receive additional antiretroviral medications, preventing conclusions on PK parameters of Tenofovir (TFV) alone (TFV results following absorption after conversion of the oral prodrug TDF).(11) Doses that are optimal for Human Immunodeficiency Virus (HIV) may not be appropriate for HBV.

When TDF is administered during pregnancy and potentially during lactation, it is important to establish the infant drug exposure. Previous human studies have shown that antiretrovirals administered to lactating mothers are present in the breast milk and have detected a low TDF breast milk concentration representing 0.03% or less of the proposed infant dosage.(13)((14) However, there is no data on this subject in therapeutic treatment of HBV infected women. In resource poor settings TDF administration will be ceased after 1 month post-partum and while

there is some data to understand what happens to viral load post cessation in non-pregnant, post-partum TDF cessation is less well understood but where immunity may differ critically.(12, 15) With breastmilk as the primary source of nutrition for babies in resource limited settings it is important to know the viral exposure from breastmilk, if any, as these settings may also have problems achieving birth dose, HBIG and the 3 dose vaccine completion.

3. Study rationale & justification

We propose a dense PK study of once daily TDF 300 mg during pregnancy given for PMTCT of HBV mono-infection. Tenofovir PK will be measured in maternal blood samples in steady-state, in the 2nd and 3rd trimesters and post-partum. The presence of HBV DNA in blood and breast milk will also be explored while women after cessation of treatment until 6 months post-partum.

4. Study Objectives and Outcome Measures

Objectives	Outcome Measures	Timepoint(s) of evaluation of this outcome measure (if applicable)
Primary Objective To measure the dense PK parameters of TFV in a steady-state during three gestational periods in TDF treated HBV mono infection	PK parameter profiles in maternal blood	Blood sampling every month and dense sampling every gestational period
Secondary Objectives To investigate the TFV concentration , breastmilk and infants To investigate if/when HBV DNA is detected in blood and breastmilk after cessation of TDF.	
 - Maternal breastmilk TFV concentrations - Milk to maternal plasma concentration ratios (M/P) - Infant plasma drug concentration HBV DNA in blood and breastmilk	At delivery and 1 month post-partum Post-partum monthly maternal blood and breastmilk samples up to 6 months.

5. Study Design

Participants with HBV mono infection and a measurable HBV DNA viral load attending SMRU antenatal clinics (ANC) on the Myanmar-Thailand border will be invited if they have a gestational age of at least 20 weeks. A total of 24 women: 12 participants enrolled in 2nd trimester (EGA ≥ 20 -<24 weeks) and 12 enrolled in 3rd trimester (EGA ≥ 28 -<36) with complete samples are required.

Women, identified by routine antenatal care screening for HBV will be invited to participate if they are HBsAg positive and meet the inclusion and exclusion criteria. Participants will be provided TDF 300mg daily and will continue TDF treatment until one month after delivery. The TFV concentrations will be measured monthly before delivery, at delivery, in cord blood and 1 and 2 months postpartum. Additional dense PK blood sampling will be done in the second and third trimester and postpartum. Breast milk samples timed with mother blood and infant blood samples will be included to measure drug concentrations in breastmilk as possible presence of HBV DNA viral in breastmilk following cessation of TDF.

The dense sampling for pharmacokinetics assessments will occur at least after 2 weeks of TDF treatment in second trimester between 22–26 weeks gestation, in third trimester between 30–38 weeks gestation, and 4 weeks postpartum. The dense sampling will entail twelve blood samples in a 24 hour period (24ml of blood in total). Women will be counseled about the importance of adherence. Direct Observed Treatment (DOT) in the 3 days prior to the dense blood sampling will be performed. The woman can choose to be admitted for these days or if a home visitor lives close enough be supervised at home.

The follow-up for women will be until 6 months post-partum, to check for flares. TFV concentrations will be collected by venous blood testing but an indwelling catheter can be used during the rich sampling 24 hour period. Infants will be followed up from delivery, and at 1, 2, 4 and 6 months of age for vaccination and growth. Infant drug exposure is measured at month 1 and HBV DNA will be measured at birth from cord blood and HBsAg by venepuncture at 2 months of age. The flow chart is available in Appendix B.

Study duration

We will enroll volunteers into this study after ethical approval. Because we will enroll subjects in gestational windows we expect the recruitment and follow up to last at least 2 years.

6 Participant identification and recruitment

6.1 Study Population

Pregnant women aged 16-49 years with confirmed HBV mono infection (identifiable from the routine care provided at SMRU clinics) will be included.

6.2 Inclusion criteria

All of the inclusion criteria must be answered as ‘yes’ to consider the participant eligible:

- Single viable pregnancy at enrollment day
- Estimated Gestational Age (EGA) ≥ 20 -<24 weeks for 2nd trimester or EGA ≥ 28 -<34 for 3rd trimester
- Willing and able to give informed consent for participation in the study
- Hepatitis B infected (HBsAg and HBeAg confirmed positive or HBsAg confirmed positive and HBV DNA detected in HBeAg negative)
- Burmese and Karen female, 16-49 years (inclusive)
- Willing to take TDF daily during pregnancy
- Plans to deliver at SMRU clinics

6.3 Exclusion criteria

If any exclusion criteria are answered as ‘yes’ the subject may not enter the study:

- Undetectable HBV DNA in HBeAg negative women
- HIV infected or other chronic illness incompatible with the study requirements or receiving Immunosuppressive therapy
- Creatinine at screening > 1 mg/dL
- Serum phosphate < 2.4 mg/dL
- History of chronic kidney disease

6.4 Co-Enrolment Guidelines

Subjects can be enrolled into any other study while participating in this study as long as it doesn't interfere with the inclusion criteria or study procedures.

6.5 Study site

The study will take place in the Shoklo Malaria Research unit (SMRU) clinics, Mae sot.

7. Study Procedures

7.1 Pre-study training

Pre-study training is an essential part of this study to ensure this study is conducted according to Good Clinical Practice (GCP) and the approved version of protocol.

7.2 Subject screening and enrolment

Records of currently pregnant women attending SMRU antenatal care clinics (ANC) will be reviewed by the doctor and those who are HBV infected will be approached. For new pregnant women attending ANC, a routine part of antenatal care (not study related) is screening at the first visit for HBV and HIV. Samples collected from women identified as HBsAg positive by routine rapid detection kit Pacific Biotech Co Ltd. (2 drops of capillary blood) at the SMRU clinics will be sent to a certified laboratory in Thailand for confirmation of HBsAg and HBeAg status (routine). When the rapid test is found positive women will be invited to learn more about the study by discussion with a trained counsellor.

After signing the informed consent form, all HBV infected subjects will be given a screening number at the time of screening. If they pass screening and are enrolled into the study, they will be given a subject number.

7.3 Study Evaluation

7.3.1 Screening Visit, Day -7

At screening visits, the subjects who are tested HBV infected and have a viable singleton pregnancy will be required to undergo the following tests and procedures:

- Obtain informed consent

- Obtain blood samples for laboratory tests; biochemistry (creatinine, phosphate, ALT), HBsAg, and HBeAg tests (and HBV DNA qualitative test if the mother is HBeAg negative)

7.3.2 Study enrollment, Day 0 (Baseline)

- The participant comes to get an ultrasound to make sure there is a single viable pregnancy. The blood tests will be checked and if the participant is eligible, they can enroll in the study. If the criteria are not met, the participant can not enroll.
- Obtain demographic information
- Perform physical examination including vital signs, height and weight
- Provide medical history including history of all medications, vitamins, and allergies
- Provide obstetric data (Symphysis fundal height, fetal gestational age and heartbeat, details of any past pregnancies, complications, place of delivery and outcome will be recorded)

7.3.3 TDF administration

Generic GPO-TDF 300mg tablet will be used for this study. TDF 300mg will be administered daily and continue until 28 days post-partum.

The subject will be counseled about the importance of adherence. For the dense PK sampling it is of great importance to be in a steady state (see 7.3.5.1 “Pharmacokinetic Evaluation). To ensure this, we will perform DOT in the 3 days prior to the dense blood sampling. The subject can choose to be admitted for DOT administration (see 8.2.4 “Blood tests”)

Adherence survey and pill count will be performed monthly when the subject returns to the clinic to ensure compliance of TDF.

7.3.4 Evaluation of TDF regimen

Subjects will have creatinine and ALT concentrations checked every month. They will be asked about other side effects like nausea, vomiting or diarrhea.

7.3.5 Follow up

7.3.5.1 Monthly follow up during pregnancy

From the time TDF is started through the end of the study, the participants will return for monthly study visits. At each visit pregnancy will be checked for maternal and fetal well-being. Obstetric follow-up at each monthly visit will include the following:

- physical examination
- vital signs and weight
- symphysis fundal height measurement
- fetal heart beat
- concomitant medications
- blood sample for biochemistry (creatinine, ALT), and HBV DNA (See details in Appendix C).

7.3.5.1.1 Pharmacokinetic Evaluation

The dense PK sampling will occur after 2 weeks of TDF treatment in second trimester between 22–26 weeks gestation and in third trimester between 30–38 weeks gestation. The blood collections (approximately 2 ml) will be taken at the following times relative to the dose of TDF: pre-dose and 0.5, 1, 1.5, 2, 3, 4, 6, 8, 12, 16, and 24 hours post-dose.

7.3.5.2 Delivery

The following will be performed at delivery:

- Physical examination, vital signs, co-medication
- Pregnancy complications and mode of delivery will be recorded.
- Anthropometric measurements of the newborn will be done in the first hour of life and will include birth weight, length, head and arm circumference, by trained staff and according to work instructions and standard operating procedures.
- Vaccination standard HB vaccine at delivery (birth dose) and at 2, 4 and 6 months post-partum will be provided to newborns of mothers with chronic HBV infection.

- HBIG will be provided to all children born to mothers in the study according to the Thai National Guidelines.
- Mother blood sample will be obtained for clinical laboratory assessments; biochemistry (creatinine, Phosphate, ALT), TDF concentration and HBV DNA.
- Cord blood sample will be obtained after the birth of the baby and before delivery of the placenta for HBV DNA and TDF concentrations, and for HBsAg and HBeAg testing.
- Breast milk collection (until 2 days post partum).
- Pill count and adherence survey
- AE and concomitant medications

7.3.5.3 Post-partum follow up of mothers

The subject will be followed up monthly until 6 month post-partum. The following procedure will be performed on the mothers:

- Physical examination and vital signs at each post-partum visit.
- TDF will be continued until one month post-partum to theoretically decrease the risk of flares as their immune system returns to baseline.
- The last dense PK sampling will occur at 4 weeks post-partum.
- At the 1 month post-partum follow up, the woman will again have dense PK sampling of her blood. A single breastmilk sample will be taken 4 hours after drug dosing.
- At the 1 month post-partum visit, Creatinine will be measured, if Creatinine is increased (\geq 1.5 times from the baseline) this will be repeated according to routine care.
- The last blood sampling on PK (single blood sample) will be at the 2 month post-partum.
- At the 1 and 4 months post-partum visits, ALT will be measured (from 5ml and 2 ml respectively). If ALT is increased with a Grade 3 or higher (described in 13.3.1) but there is not a true flare, the ALT will be repeated at 6 months post partum.

- At each post-partum visit month 1 to month 6, breastmilk samples will be collected and blood samples will be collected for HBV DNA tests

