11.5 Subject Management of Adverse Events

All AEs will be treated as clinically indicated, and if concomitant treatment is given this will be recorded on the Concomitant Medication CRF. If necessary, participants will be referred for specialist care/advice.

The subject will be followed and treated by the research team until the clinical or laboratory AE has resolved or stabilised. The physician should perform any tests that are clinically indicated.

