13.3 Risks

13.3.1 Risks of oral TDF

TDF is globally being used in pregnant women for prevention of mother to child transmission of HIV. It is generally well tolerated with the most common adverse reactions identified from any of the large controlled clinical trials include rash, diarrhea, headache, pain, depression, asthenia, and nausea.(16, 17)

Other side effects are:

- Kidney failure defined as:

- A rise in serum creatinine \geq 1.5 times from the baseline OR
 - An absolute rise in serum creatinine of \geq 26.5 $\mu\text{ml/L}$ (\geq 0.3 mg/dl) within 48 hours

- ALT rise to Grade 3.

Grade 3 or higher is >5 x upper limit of normal (ULN) if baseline levels were below the ULN; or if baseline levels were $>$ ULN and, then grade 3 or higher is >3.5 x baseline value. The normal value of ALT will be defined as 0-31 U/L.(18)

- Hepatic flare

A tangible adverse consequence that requires further study is the potential for hepatitis flare following discontinuation of therapy in the mother. All women will continue on study until the 4 month post-partum visit. At the 1 and 4 months post-partum visits ALT will be measured (from a 5ml and 2 ml blood sample respectively). If 3 months after stopping TDF, a flare is detected (ALT >5 x baseline if this was increased at baseline or >10 x the upper limit of normal with no alternative diagnosis) the woman will continue to be monitored until resolution of the flare. If the flare worsens or does not resolve they will be placed on anti-HBV therapy and be reviewed by a physician. If ALT is increased but there is not a true flare,

(ALT>3.5x baseline if this was increased at baseline or >5x the upper limit of normal), they will be followed for an additional 6-9 months and repeat ALT testing done at 6 months.

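### The 1-month post-partum creatinine is judged against a pregnancy baseline, and no off-drug, non-pregnant creatinine is scheduled for all women, so a rise at that visit cannot be reliably attributed

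*Combined protocol and SAP*

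**What the plan says.** **Baseline.** Section 7.3.1 (Day -7) provides: "Obtain blood samples for laboratory tests; biochemistry (creatinine, phosphate, ALT"). Eligibility in section 6.2 requires "Single viable pregnancy at enrollment day". Every baseline creatinine is therefore a pregnancy value.

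**During treatment.** Section 7.3.4 has creatinine checked every month, under the heading for evaluating the TDF regimen. Section 7.3.5.2 adds a delivery sample: "Mother blood sample will be obtained for clinical laboratory assessments; biochemistry (creatinine, Phosphate, ALT"). Section 7.3.3 ends TDF at 28 days post-partum.

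**One month post-partum.** Section 7.3.5.3: "At the 1 month post-partum visit, Creatinine will be measured, if Creatinine is increased" (to 1.5 or more "times from the baseline) this will be repeated according to routine care").

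**Definition.** Section 13.3.1 lists, among the side effects of TDF, "Kidney failure defined as" either that same ratio or an absolute rise of at least 0.3 mg/dl within 48 hours. It sets no separate post-partum reference.

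**Afterwards.** Section 7.3.5.3 schedules no further creatinine for all women. The Appendix C chemistry rows are displaced in the text version, but under either alignment the creatinine row has no mark after 1 month post-partum. ALT is treated differently: "At the 1 and 4 months post-partum visits ALT will be measured (from a 5ml and 2 ml blood sample respectively"). If a raised creatinine is judged an adverse event, section 11.5 applies: "The subject will be followed and treated by the research team until the clinical or laboratory AE has resolved or stabilised".

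**The concern.** Between the baseline and the 1-month sample, two things can change: the woman has been exposed to TDF, and she is no longer pregnant. A ratio of the two values mixes both. The monthly and delivery samples help to date a rise. They are taken on drug, in pregnancy or at birth, so they do not separate the causes of a rise first seen at 1 month.

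A value that is both off drug and non-pregnant would help, but only women who cross 1.5 times baseline get one, at an unspecified time. Women below the threshold supply none. The cohort therefore never shows how far creatinine moves when pregnancy ends, and that movement is what a physician needs to read a flagged woman's result.

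The judgement at stake is the one in section 11.8, where team physicians decide whether kidney failure is present. Section 8.5 points staff to the definition in section 13.3.1. An end-of-pregnancy change could be labelled TDF toxicity, or a real drug effect could be dismissed as the end of pregnancy. Creatinine after TDF is also unrecorded in women who are not flagged.

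**Working it through.** **The plan's own figures.** The documents give no figure for post-partum creatinine. The only derived number in section 12.1 is 60 dense curves, which reproduces as 12 × 3 + 12 × 2 = 60. It does not bear on this point. Only the cohort size, 24, is used below.

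**Inputs.**
- From the documents: threshold 1.5 (sections 7.3.5.3 and 13.3.1); 24 women (section 12.1).
- Assumed: no renal injury; the 1-month/baseline ratio is log-normal; median shift *r* of 1.00, 1.10 or 1.25; CV of the ratio 10, 15 or 20%.

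**Step 1. Uninjured women who cross the threshold.** With σ = √ln(1 + CV²), σ is 0.0998, 0.1492 and 0.1980. Then P(ratio ≥ 1.5) = 1 − Φ(ln(1.5/*r*)/σ). For example, with *r* = 1.25 and CV 20%, ln(1.2)/0.1980 = 0.921, so P = 17.86% and 24 × 0.1786 = 4.29 women.

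| Shift | CV 10% | CV 15% | CV 20% |
|---|---|---|---|
| 1.00 | 0.00% (0.00 women) | 0.33% (0.08) | 2.03% (0.49) |
| 1.10 | 0.09% (0.02) | 1.88% (0.45) | 5.87% (1.41) |
| 1.25 | 3.38% (0.81) | 11.08% (2.66) | 17.86% (4.29) |

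The range is 0 to about 4.3 of 24. The top needs both the largest shift and the largest CV.

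**Step 2. What a 4-month value adds for the cohort.** The 95% confidence factor for the geometric mean 4-month/baseline ratio in 24 women is exp(t(0.975, 23) × σ/√24). At CV 10% this is exp(2.069 × 0.0998/4.899) = 1.043. At CV 15% and 20% it is 1.065 and 1.087. The missing shift would be known to within a factor of about 1.04 to 1.09.

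**Step 3. What it adds for a flagged woman.** Median ratios with an assumed shift of 1.25:

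| Situation | 1-month/baseline | 4-month/baseline | 1-month/4-month |
|---|---|---|---|
| No injury | 1.25 | 1.25 | 1.00 |
| Transient 1.5-fold injury | 1.25 × 1.5 = 1.88 | 1.25 | 1.50 |
| Persistent 1.5-fold injury | 1.88 | 1.88 | 1.00 |

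The 1-month/4-month ratio separates transient injury from the rest. The 4-month/baseline ratio, set against the cohort shift, separates persistent injury from the end of pregnancy. Neither ratio is enough alone.

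**Step 4. Check of reading rules by simulation.** Assumptions: 4,000,000 draws, no injury, each sample with log SD σ/√2, equal 1-month and 4-month means.
- *Reading only whether the 4-month value is still at least 1.5 times baseline.* At shift 1.25 and CV 20%, the 4.3 flagged women split into about 2.5 called resolved off drug and 1.8 called possible persistent injury. At CV 10%, 0.81 splits into 0.64 and 0.17. No uninjured woman is assigned to the end of pregnancy, so this rule is inadequate.
- *Requiring the 1-month value to be at least 1.5 times both baseline and the 4-month value before calling it a reversal off drug.* Over all nine combinations, at most about 0.3 of 24 uninjured women meet this.

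A usable rule therefore needs the 1-month/4-month ratio and the cohort shift together.

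**The case against.** The strongest reply is that the plan does order a later creatinine for the women who matter. Anyone at 1.5 times baseline or more is repeated. TDF has ended at 28 days, so the repeat would normally be off drug and not pregnant, and section 11.5 follows a laboratory adverse event until it resolves or stabilises. A reader might infer that no later creatinine exists and that attribution is impossible. The documents do not support that. A fall after stopping would point towards TDF, and section 11.3 grades relatedness separately, with not related as an option.

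This stands as far as it goes, but the repeat has no date and could come before any recovery. A stable repeat is also ambiguous: it fits the end of pregnancy and persistent injury equally. The cohort shift that would tell them apart comes from women who are not repeated.

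Three further points are fair.
- The documents nowhere say that creatinine rises after pregnancy. If the shift is nil, the expected number of false flags is 0 to 0.5 of 24.
- No renal endpoint or event analysis is planned. Section 12.3.1 only summarises biochemistry, and TDF stops at about this visit whatever the result.
- Section 8.2.4 (Blood tests) keeps leftover serum or plasma for clarification, so a later measurement might be possible. The plan does not commit to one.

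Section 7.3.4 gives no end date for the monthly check. If the sponsor means it to run to 6 months, the gap closes, but section 7.3.5.3 and Appendix C then need correcting to say so.

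**Conclusion.** The point holds as a minor one. The 1-month creatinine is compared with a pregnancy value by the ratio that defines kidney failure. No off-drug, non-pregnant value is scheduled for the whole cohort, and the conditional repeat has neither a time nor a comparator. Attribution of a 1-month rise is therefore unreliable, though not impossible.

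The size rests wholly on assumed inputs: 0 to 4.3 of 24 uninjured women flagged for shifts of 1.0 to 1.25 and CVs of 10 to 20%. It is not a prediction of false kidney failures.

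A reader might also infer that flagged women are left clinically unprotected or that the PK results are compromised. Neither follows: the repeat and section 11.5 cover the first, and creatinine labelling does not enter the PK endpoints. What is affected is safety labelling and knowledge of renal recovery off drug.

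**What to change.** Keep the 1.5-fold repeat trigger and the section 11.5 follow-up as they are. Add creatinine for all women to the 2 ml sample already drawn for ALT at 4 months post-partum, about 3 months off TDF, and enter it in section 7.3.5.3, section 13.3.1 and Appendix C.

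In section 12.3.1, report the 1-month value against both the pregnancy baseline and the 4-month value, and report the cohort's 4-month/baseline ratio. In section 13.3.1, state that a post-partum value is not labelled TDF kidney failure on the pregnancy-baseline ratio alone, and that a flagged 1-month value is read as follows:

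- 1-month/4-month at least 1.5: a rise that reversed off drug; grade relatedness under section 11.3.
- 1-month/4-month near 1, with 4-month/baseline in line with the cohort shift: consistent with the end of pregnancy.
- 4-month/baseline well above the cohort shift: possible persistent injury; continue section 11.5 follow-up. Such a value follows TDF exposure and is not a clean reference.

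The limits for near 1 and well above should be fixed before the data are seen, and values that fit none of the three reported as indeterminate.

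The cost is about 24 assays, no extra venepuncture and a few lines of text. The repeat test is not delayed, but final classification of a raised 1-month value may wait up to 3 months.

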7.3.5.4 Post partum follow up of mothers with flare

The majority (95%) of the women will have the study endpoint at 6 months. However, if flare is detected, these women will be followed for a further 6-9 months and provided with drug therapy where monitoring shows it is required.

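### Women are followed to month 6 to check for flares, but sections 7.3.5.3 and 13.3.1 give a woman who never reached Grade 3 ALT no scheduled ALT after month 4

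*Combined protocol and SAP*

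**What the plan says.** Section 5 gives the purpose of maternal follow-up: "The follow-up for women will be until 6 months post-partum, to check for flares". Section 7.3.3 fixes the end of treatment: "TDF 300mg will be administered daily and continue until 28 days post-partum".

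Section 7.3.5.3 sets the post-partum ALT schedule: "At the 1 and 4 months post-partum visits, ALT will be measured". If ALT is Grade 3 or higher without a true flare, "the ALT will be repeated at 6 months post partum". Blood is drawn throughout: "At each post-partum visit month 1 to month 6, breastmilk samples will be collected and blood samples will be collected for HBV DNA tests".

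Section 13.3.1 repeats the schedule ("At the 1 and 4 months post-partum visits ALT will be measured") and defines a flare by ALT: more than 5 times a raised baseline, or more than 10 times the upper limit of normal with no other diagnosis. It refers to a flare found 3 months after stopping TDF, and it says "All women will continue on study until the 4 month post-partum visit".

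On extended follow-up, section 7.3.5.4 says that "if flare is detected, these women will be followed for a further 6-9 months". Section 13.3.1 monitors a flare until it resolves, and gives an additional 6-9 months to women whose ALT is raised without a true flare.

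**The concern.** A flare defined by ALT can be found on schedule only where an ALT is scheduled. The month 1 value falls at the end of treatment, so it cannot show what happens off drug. That leaves month 4 as the one off-drug value for every woman. A flare that begins after month 4, in a woman with no earlier Grade 3 value, would come to light only through symptoms or a test ordered on clinical grounds, although she still attends and gives blood at months 5 and 6. Longer follow-up, and therapy where monitoring shows it is needed (7.3.5.4), both depend on detection.

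Staff also lack one consistent instruction. The safety net in section 8.5 sends them to 13.3.1 for flares, and that is the section with the month 4 sentence. They need to know when flare checking ends and who receives the extra 6-9 months.

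**Working it through.** The plan states no figure to reproduce. The check compares the sections and does arithmetic on the visit times.

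**Inputs.** TDF stops on day 28 (7.3.3). Visits are monthly to month 6 (7.3.5.3). ALT for all women is at months 1 and 4 (7.3.5.3, 13.3.1). There are 24 women (12.1). The month 4 ALT sample is 2 mL (7.3.5.3). Total maternal blood is 144 mL for trimester 2 entry and 96 mL for trimester 3 entry (8.2). Assumptions: one month = 365.25/12 = 30.44 days, and visits fall on their nominal dates.

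**Timing off drug.**
- Month 2: 2 × 30.44 − 28 = 32.9 days
- Month 4: 4 × 30.44 − 28 = 93.8 days
- Month 6: 6 × 30.44 − 28 = 154.6 days
- Month 4 to month 6: 60.9 days, and 60.9/154.6 = 39% of off-drug follow-up

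Of the five monthly visits after TDF stops (months 2 to 6), one has an ALT for every woman.

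**Longest wait from the start of a rise to the next scheduled ALT.**

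| ALT for all women at | Longest wait |
|---|---|
| month 4 | 93.8 days up to month 4; no ALT after it |
| months 4 and 6 | max(93.8, 60.9) = 93.8 days |
| months 2, 4 and 6 | max(32.9, 60.9, 60.9) = 60.9 days |

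A month 6 ALT therefore closes the gap after month 4 but leaves the first three months off drug as they are. Only a month 2 ALT shortens that wait.

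**Who gets a month 6 ALT on the text.** With the upper limit of normal at 31 U/L and a normal baseline, the trigger is above 5 × 31 = 155 U/L and a flare is above 10 × 31 = 310 U/L. A month 4 value raised but at or below 155 U/L brings no repeat. Under 7.3.5.3 the trigger can follow the month 1 or the month 4 test, so a woman at Grade 3 at month 1 may have a month 6 ALT even if month 4 is normal. A woman with a true flare at month 4 is monitored until resolution. The uncovered group is those who never met the trigger.

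**Sections side by side.**
- End of follow-up: month 6 in sections 5, 7.3.5.3 and 7.3.5.4; month 4 in the on-study sentence of 13.3.1.
- Extra 6-9 months: for a flare in 7.3.5.4; for raised ALT without a true flare in 13.3.1.

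**The case against.** The strongest reply is that month 6 ALT may already be intended for everyone. The ALT row of Appendix C ends in a footnoted mark, and the footnote says only that follow-up goes on where a flare is suspected or confirmed. It does not make the test conditional. On that reading the 61-day gap disappears and what remains is a mismatch between the schedule and the text. This stands as a possibility. The row has lost a cell in extraction, so the column of the mark is inferred, and Table 1 is not in the text available.

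Monthly ALT could also be argued from 7.3.4, from 7.3.5.1 (monthly visits to the end of the study, with ALT) and from 8.2.1. This is weaker. Section 7.3.4 concerns evaluation of the TDF regimen, 7.3.5.1 is headed as pregnancy follow-up, and 8.2.1 defers to Table 1. Section 7.3.5.3 is the specific post-partum rule, and its conditional month 6 repeat would be redundant if ALT were monthly.

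Physical examination and adverse-event review do continue at months 5 and 6, but neither includes a scheduled ALT.

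Some stronger readings are tempting but unsupported:
- A reader might infer a third flare window from the 3 months in section 13.2. That sentence covers women who withdraw, so it is not a conflict.
- A reader might infer that the two extension rules contradict each other. They name different groups, but neither denies follow-up to the other's group.
- A reader might infer that flares will be missed at some rate. The documents give neither onset nor duration of flares, so no number can be stated.

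**Conclusion.** The point holds as a maternal-safety and consistency matter. On 7.3.5.3 and 13.3.1, one off-drug ALT is scheduled for every woman, about 94 days after TDF stops, and a woman who never reached the Grade 3 trigger has none in the last 61 days. This rests on those two sections being the operative post-partum rule and on nominal visit dates. If Appendix C or Table 1 does intend month 6 ALT for all, the monitoring gap falls away, but the two sections still need correcting to match. The month 4 sentence in 13.3.1 conflicts with sections 5, 7.3.5.3 and 7.3.5.4 on either reading, and the extension rule remains incomplete in each place it appears. Flare is not a listed endpoint.

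**What to change.** 1. In 7.3.5.3 and 13.3.1, schedule ALT for all women at month 6 as well as months 1 and 4, on blood from the visit already bled for HBV DNA. Make the Appendix C mark unconditional and check Table 1 against it.
2. In 13.3.1, change the on-study sentence from the 4 month to the 6 month visit, and let the flare rule apply to the month 6 value as well as the one 3 months after stopping.
3. State one extension rule, in the same words in 7.3.5.4 and 13.3.1, covering both a flare and a Grade 3 or higher ALT without a flare.

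**Cost.** At most 24 × 1 = 24 routine assays. At the protocol's month 4 volume this is 2 mL per woman: 2/144 = 1.4% or 2/96 = 2.1% of the stated totals. No extra visit or venepuncture is needed, though a plain tube may be. The blood total in the information sheet needs updating. If month 6 ALT for all is already intended, only the text changes.

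**Optional, for the clinical team.** Adding month 2 as well would bring the longest wait down to 61 days, for at most 24 × 2 = 48 assays and 4 mL per woman in all (4/144 = 2.8% or 4/96 = 4.2%).
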